## 6.5 Dose escalation and dose modification

Investigational or other study treatment dose adjustments and/or interruptions are not permitted.

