### 6.6.3 Emergency breaking of assigned treatment code

Emergency code breaks must only be undertaken when it is required to do so in order to treat the participant safely. Blinding codes may also be broken after a participant discontinues treatment due to disease progression if deemed essential to allow the investigator to select the participant's next treatment regimen, and after discussion and agreement with the sponsor. Most often, study treatment discontinuation and knowledge of the possible treatment assignments are sufficient to treat a study participant who presents with an emergency condition. Emergency treatment code breaks are performed using the NIRT. When the investigator contacts the system to break a treatment code for a participant, he/she must provide the requested participant identifying information and confirm the necessity to break the treatment code for the participant. The investigator will then receive details of the investigational drug treatment for the specified participant and a fax or email confirming this information. The system will automatically inform the Novartis monitor for the site and the study team that the code has been broken.

It is the investigator's responsibility to ensure that there is a dependable procedure in place to allow access to the NIRT at any time in case of emergency. The investigator will provide:

- protocol number
- study drug name (if available)
- participant number

In addition, oral and written information to the participant must be provided on how to contact his/her backup in cases of emergency, or when he/she is unavailable, to ensure that un-blinding can be performed at any time.

An assessment will be done by the appropriate site personnel and sponsor after an emergency unblinding to assess whether or not study treatment should be discontinued for a given participant and, if applicable, whether the participant can continue with follow up assessments.

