## 9 Study discontinuation and completion

### 9.1 Discontinuation and completion

#### 9.1.1 Study treatment discontinuation and study discontinuation

Discontinuation of study treatment for a participant occurs when study treatment is stopped earlier than the protocol planned duration and can be initiated by either the participant or the investigator.

The investigator must discontinue study treatment for a given participant if, he/she believes that continuation would negatively impact the participant's well-being.

Study treatment must be discontinued under the following circumstances:

- Participant/guardian decision
- Pregnancy
- Use of prohibited treatment as per recommendations in the prohibited medication [Section 6.2.2](#) and rescue medication [Section 6.2.3](#)
- Any situation in which study participation might result in a safety risk to the participant
- Following emergency unblinding
- Severe hypersensitivity reaction occurs, including any of the following: anaphylaxis, fever, chills, urticaria, dyspnea, headache, myalgia, hypotension. Immediate interruption of the infusion or injection to administer study treatment is required in such cases.
- For liver events, please see [Section 10.2.1](#). For renal events, please see [Section 10.2.2](#)
- If a liver or renal event occurs, follow guidelines outlined in [Section 16.2](#) and [Section 16.3](#) regarding discontinuation of study treatment.

The reasons for treatment discontinuation must be collected in line with the intercurrent events introduced in [Section 2.1](#) and the "treatment" attribute described in [Section 2](#) and [Section 6](#).

If discontinuation of study treatment occurs, the investigator should make a reasonable effort to understand the primary reason for the participant's premature discontinuation of study treatment and record this information.

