### 10.2.1 Liver safety monitoring

To ensure participant safety and enhance reliability in determining the hepatotoxic potential of an investigational drug, a standardized process for identification, monitoring and evaluation of liver events has to be followed.

Please refer to [Table 16-1](#) for complete definitions of liver laboratory triggers.

Once a participant is exposed to study treatment, every liver event defined in [Table 16-1](#) should be followed up by the investigator or designated personnel at the trial site, as summarized below. Additional details on actions required in case of liver events are outlined in [Table 16-1](#). Repeat liver chemistry tests (i.e. ALT, AST, TBL, PT/INR, ALP and G-GT) to confirm elevation within 48-72 hours.

- These liver chemistry repeats will be performed using the central laboratory. If results will not be available from the central laboratory in timely manner, then the repeats can also be performed additionally at a local laboratory to monitor the safety of the participant. If a liver event is subsequently reported, any local liver chemistry tests previously conducted that are associated with this event should have results recorded on the appropriate eCRF.
- If the initial elevation is confirmed, close observation of the participant will be initiated, including consideration of treatment interruption if deemed appropriate.
- Discontinuation of the investigational drug (refer to [Section 9.1.1](#) Discontinuation of study treatment section), if appropriate.
- Hospitalization of the participant if appropriate.
- Causality assessment of the liver event.
- Thorough follow-up of the liver event should include:
  - Repeating liver chemistry tests two or three times weekly. Testing should include ALT, AST, ALP, PT/INR, and GGT. If total bilirubin is elevated  $> 2 \times$  Upper Limit of Normal (ULN), fractionation into direct and indirect bilirubin is required. To rule out muscular origin of transaminase elevations, CPK should be measured along with liver chemistry tests. Frequency of retesting can decrease to once a week or less if abnormalities stabilize or the study drug has been discontinued and the participant is asymptomatic. Retesting should be continued up to resolution.
  - Obtaining a more detailed history of symptoms and prior or concurrent diseases.

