**Table 16-2 Actions required for Liver Events**

| Criteria   | Actions required  |
|--|---|
| Potential Hy's Law case  |   |
| ALT or AST elevation with coagulopathy   |   |
| ALT or AST elevation accompanied by symptoms   | 
 
• Discontinue the study treatment immediately
 
• Hospitalize, if clinically appropriate
 
• Establish causality
 
• Complete CRFs per liver event guidance*
 
   |
| Isolated ALT or AST elevation $> 8 \times \text{ULN}$  |   |
| Jaundice   |   |
| Isolated ALT or AST elevation $> 5 \text{ to } \leq 8 \times \text{ULN}$                           | 
 
• If confirmed, consider interruption or discontinuation of study drug
 
• If elevation persists for more than 2 weeks, discontinue the study drug
 
• Establish causality
 
• Complete CRFs per liver event guidance*
 
   |
| Isolated ALT or AST elevation $> 3 \text{ to } \leq 5 \times \text{ULN}$ (patient is asymptomatic) | Monitor liver chemistry tests two or three times weekly   |
| Isolated ALP elevation   | 
 
• Repeat liver chemistry tests within 48-72 hours
 
• If elevation is confirmed, measure fractionated ALP; if <math>>50\%</math> is of liver origin, establish hepatic causality
 
• Complete CRFs per liver event guidance*
 
 |
| Any AE potentially indicative of liver toxicity  | 
 
• Consider study treatment interruption or discontinuation
 
• Hospitalize if clinically appropriate
 
• Complete CRFs per liver event guidance*
 
  |

\*Liver event guidance for CRF completion is available in the CRF Completion Guidelines.

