## 16.3 Appendix 3: Specific Renal Alert Criteria and Actions and Event Follow-up

**Table 16-4 Specific Renal Alert Criteria and Actions**

| Renal Event  | Actions   |
|--|---|
| Confirmed serum creatinine increase 25 – 49%   | 

Consider causes and possible interventions

Follow up within 2-5 days

  |
| Serum creatinine increase 50 % +
OR if <18 years old, eGFR 35 mL/min/1.73 m    | 

Consider causes and possible interventions

Repeat assessment within 24-48h if possible

Consider drug interruption or discontinuation unless other causes are diagnosed and corrected

Consider patient hospitalization and specialized treatment

 |
| New onset dipstick proteinuria $\geq 3^+$
OR
Protein-creatinine ratio (PCR) $\geq 1\text{g/g Cr}$ (or mg/mmol equivalent as converted by the measuring laboratory) | 

Consider causes and possible interventions

Assess serum albumin & serum total protein

Repeat assessment to confirm

Consider drug interruption or discontinuation unless other causes are diagnosed and corrected

                            |
| New onset hematuria $\geq 3^+$ on urine dipstick   | 

Repeat assessment to confirm

Distinguish hemoglobinuria from hematuria

Urine sediment microscopy

Assess sCr

Exclude infection, trauma, bleeding from the distal urinary tract/bladder, menstruation

Consider bleeding disorder

  |

+ Corresponds to KDIGO criteria for Acute Kidney Injury

Additional specialized assessments are available to assess renal function or renal pathology.  
*(Note: In exceptional cases, when a nephrologist considers a renal biopsy, it is recommended to make slide specimen available for evaluation by the RSG to potentially identify project-wide patterns of nephrotoxicity.)*

- Whenever a renal event is identified, a detailed patient history and examination are indicated to identify and potentially eliminate risk factors that may have initiated or contributed to the event:
- Blood pressure assessment (after 5-minute rest, with an appropriate cuff size)
- Signs and symptoms like fever, headache, shortness of breath, back or abdominal pain, dysuria or hematuria, dependent or periorbital edema

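### Protocol 6.5 forbids an interruption that the liver and renal rules offer, and 9.1.1 requires a stop after emergency unblinding that 6.6.3 leaves to assessment

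*Protocol*

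**What the plan says.** **Interruption of study treatment.** The whole of Protocol Section 6.5 is one sentence: "Investigational or other study treatment dose adjustments and/or interruptions are not permitted". It has no exception and no cross-reference.

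Four other places treat interruption as available:

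- Section 10.2.1, on liver events: "If the initial elevation is confirmed, close observation of the participant will be initiated, including consideration of treatment interruption if deemed appropriate".
- Table 16-2, isolated ALT or AST above 5 and up to 8 times ULN: "If confirmed, consider interruption or discontinuation of study drug". The row for any adverse event that may indicate liver toxicity says: "Consider study treatment interruption or discontinuation".
- Table 16-4, in both the 50% creatinine-increase row and the proteinuria or protein-creatinine ratio row: "Consider drug interruption or discontinuation unless other causes are diagnosed and corrected".
- Section 10.1.1 lists interruption or withdrawal of the investigational treatment among the recordable actions taken for an adverse event.

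**Emergency unblinding.** Section 9.1.1 opens a list with "Study treatment must be discontinued under the following circumstances", and one entry reads "Following emergency unblinding". Section 6.6.3 says that the appropriate site personnel and the sponsor will make an assessment "after an emergency unblinding to assess whether or not study treatment should be discontinued for a given participant".

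**The concern.** These are working instructions on when a participant's treatment may be paused or must be stopped. An investigator with a confirmed transaminase or creatinine rise who pauses dosing under the appendix tables has done something that Section 6.5 forbids. An investigator who keeps a participant on treatment after the Section 6.6.3 assessment has departed from the mandatory list in Section 9.1.1. In both cases the site has followed one part of the protocol and breached another. What is at stake is whether sites know what they may do in a safety event, and whether such cases are recorded as deviations consistently. Some variation between sites is already built into wording that leaves the decision to judgement. The contradiction adds a further source of variation, because it depends on which section a site opens.

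**Working it through.** No formula applies, because the point rests on no rate, power or sample size. The check sets the passages side by side and asks whether any text decides between them.

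**Pair (a): interruption**

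| Place | Position on interruption |
|---|---|
| 6.5 | Banned, no exception |
| 10.2.1 | May be considered once a liver elevation is confirmed |
| Table 16-2 | Offered as an alternative to discontinuation in 2 rows |
| Table 16-4 | Offered as an alternative to discontinuation in 2 rows |
| 10.1.1 | A recordable action |

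Table rows:

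- Table 16-2 has 9 criteria rows. Two offer interruption (ALT/AST above 5 and up to 8 times ULN; any adverse event that may indicate liver toxicity). Five fall under immediate discontinuation (potential Hy's Law, coagulopathy, symptoms, above 8 times ULN, jaundice). Two have neither (above 3 and up to 5 times ULN; isolated ALP). 2 + 5 + 2 = 9.
- Assigning five rows to immediate discontinuation reads a merged cell from the layout. The two rows that offer interruption do not depend on that reading.
- Table 16-4 has 4 rows. Two offer interruption (creatinine increase of 50%; proteinuria or protein-creatinine ratio) and two do not (creatinine increase of 25 to 49%; hematuria).
- Together, 2 + 2 = 4 of 9 + 4 = 13 rows offer what 6.5 bans.

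This count describes the tables only. Section 10.2.1 introduces its follow-up steps for every liver event defined in Table 16-1, and its interruption step applies once an elevation is confirmed. It therefore also reaches events such as ALT/AST above 3 and up to 5 times ULN and isolated ALP elevation, whose own rows in Table 16-2 do not mention interruption.

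Does any text decide? The liver and renal pointers in 9.1.1 sit in the list of reasons for discontinuation. The one that sends sites to Sections 16.2 and 16.3 does so on discontinuation only. Neither pointer mentions interruption or lifts the ban in 6.5. The requirement in 9.1.1 to interrupt an infusion or injection during a severe hypersensitivity reaction is a separate matter, because it accompanies mandatory discontinuation.

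**Pair (b): emergency unblinding**

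| Place | Position after an emergency unblinding |
|---|---|
| 9.1.1 | Discontinuation mandatory |
| 6.6.3 | Site and sponsor assess whether to discontinue |

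Both address a participant unblinded in an emergency while on treatment. If stopping is mandatory, the assessment in 6.6.3 has nothing to decide about treatment. Section 9.1.1 later refers the reader to 6.6.3, but only for the case where a code break has led to discontinuation, and it does not say which passage governs. Code breaks made after a participant has already stopped for disease progression, which 6.6.3 also allows, are outside this pair.

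**The case against.** The strongest reply is that the instructions can all be obeyed at once. Every interruption passage is permissive, so a site that considers interruption and does not use it complies with 6.5, 10.2.1 and both tables. A site that makes the 6.6.3 assessment and then discontinues complies with 9.1.1 as well. This stands. A reader might infer that the rules are impossible to follow together, but the documents do not support that. They show an option and a discretion that cannot be used without a breach.

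A second reply is that participants are protected on either reading. Section 9.1.1 separately requires discontinuation when continuing would harm the participant or when participation may pose a safety risk, and Section 14.1 expects immediate safety action even where it departs from the protocol. This also stands, and it limits the consequence. It does not remove the inconsistency, because Section 14.1 handles such action as a deviation to be notified. An action offered in the protocol's own safety tables should not need that route.

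A third reply is that the specific rule governs the general one, so sites would work from the appendices. That is a plausible reading of practice, but the public text does not state it. It also does not help with pair (b), where both sections speak directly about emergency unblinding. Sponsor involvement in the 6.6.3 assessment would reduce drift between sites, but it does not settle which rule applies.

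**Conclusion.** The point holds in limited form. Two pairs of treatment-stopping instructions are inconsistent: 6.5 against 10.2.1 and Tables 16-2 and 16-4, and 9.1.1 against 6.6.3. In each pair, one section offers an option or discretion that the other closes.

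Two stronger inferences are not supported:

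- **That the conflict is confined to four table rows and the other nine are clear.** Section 10.2.1 reaches other confirmed liver elevations, so the row count does not measure the conflict.
- **That the primary result is affected.** The replacement rule in Section 9.1.1.1 counts a participant as evaluable with at least 3 of 4 doses, so a missed dose would count against that threshold. The dosing interval is redacted, so the documents do not show whether an interruption would cost a scheduled dose. No endpoint effect is claimed.

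The number of participants affected cannot be derived from the documents. The conclusion assumes that no redacted passage sets an order of precedence. The sections in conflict show no gap and no pointer to such a passage. This should be corrected, but it does not call the design or the analysis into question.

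**What to change.** Reconcile Section 6.5 with Section 10.2.1 and Tables 16-2 and 16-4, and reconcile Section 9.1.1 with Section 6.6.3. State each rule once and have the other sections refer to it. Check that the action categories in Section 10.1.1 agree with the result. Which rule applies is for the sponsor's clinical team to decide, and this review does not propose one.

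The textual change is small, but it is not free of process. Section 14.1 requires a written protocol amendment approved by the sponsor, by health authorities where required, and by the IRB/IEC before implementation. No extra procedures or participants are needed.

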## 6.6 Additional treatment guidance

### 6.6.1 Treatment compliance

Study medication will be administered at site. Any deviations from protocol mandated dose are to be recorded in eCRF.

Pharmacokinetic parameters (measures of treatment exposure) will be determined in all participants treated with CMK389 as detailed in [Section 8.5.2](#).

### 6.6.2 Recommended treatment of adverse events

At present there is insufficient information to provide specific recommendations regarding treatment of adverse events (AEs), as no specific AE have been detected with CMK389. Participants are required to undergo observation for maximum of one hour post-infusion prior to leaving site (or longer if deemed necessary by the investigator).

**Acute infusion or hypersensitivity reactions:** In the event of an acute infusion or hypersensitivity reaction, the investigator should consider the criteria for treatment discontinuation ([Section 9.1.1](#)), and the participant should be treated with antihistamines and glucocorticoids. Depending on severity, participants may also require supplemental oxygen, volume expansion, catecholamines and transfer to an intensive care setting. Plasmapheresis to decrease the systemic concentration of CMK389 may be considered dependent on the participant's condition. Participants should be observed for at least four hours after resolution of signs and symptoms; and those who have experienced severe infusion reactions should be closely observed for 24 hours after resolution because of the risk for a biphasic episode.

**Infections:** In the event of an infection, the investigator should consider the criteria for treatment discontinuation ([Section 9.1.1](#)), as well as consider early treatment with specific antimicrobial therapy on the basis of clinical diagnosis or suspicion thereof (e.g., antiviral treatment for herpes simplex or zoster) in consultation with infectious disease experts, as appropriate.

Medication used to treat AEs must be recorded on the appropriate eCRF.

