The study population of adult participants with moderate to severe AD is the target population for biologics (Beck et al 2014, Simpson et al 2016). To be eligible for inclusion in this trial, patients need to have an AD severity defined by an IGA score of moderate to severe and an EASI score of at least 12 as well as a minimum of 3 in the pruritus numerical rating scale (NRS). This minimum score is a bit lower than previous large trials in moderate to severe AD (inclusion criteria of EASI 16, see Simpson et al 2016, Guttman-Yassky et al 2020a, Guttman-Yassky et al 2020b) in order to facilitate recruitment without compromising the scientific outcome. Furthermore, a similar threshold has also been used previously in other Phase 2 trials with biologics (Wollenberg et al 2019 and Simpson et al 2019). Prior to enrollment in this trial treatments of AD and systemic immunosuppressives, including steroids, are washed out, using typical and relevant wash out periods. Only topical non medicated emollients are allowed to be used.

This study is only open for adult participants, as safety data for a younger populations have not yet been collected and preliminary efficacy in adults is not yet established. At the time of protocol preparation, only adult healthy volunteers have been exposed to CMK389, and a proof

of concept trial in adult participants in pulmonary sarcoidosis is planned to be conducted in parallel.

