#### **4.5 Risks and benefits**

CMK389 is a CCI targeting IL-18, a mechanism of action (MoA) that has not yet been tested in AD. There is thus no proven direct medical benefit for participants who will participate in this study as this is the first time CMK389 is administered to AD participants.

Commercially Confidential Information

CMK389 has not yet been tested in any studies in patients,

Commercially Confidential Information

No clear dose relationship was established for adverse events or organ classes such as infections, or gastro-intestinal disorders, nor in safety laboratory monitoring.

Clinical studies with compounds with a similar MoA, such as Interleukin-18 Binding Protein (IL-18BP) or IL-18 antagonists (such as tadekinig, GSK-1070806 or AEVI-007/MEDI2338) have been conducted in adult Still's disease (AOSD, [Gabay et al 2018](#), [Kiltz et al 2020](#)). Tadekinig is currently in later stage development in macrophage activation syndrome associated with NLR family CARD domain containing 4 (NLRC4) mutation and X-linked inhibitor of apoptosis protein (XIAP) deficiency (ClinicalTrials.gov Identifier: NCT03113760). Other completed studies include chronic obstructive pulmonary disease (COPD, NCT01322594), diabetes ([McKie et al 2016](#)) or transplant participants (NCT02723786). Studies in Crohn's disease and Behcet disease are currently running or of unknown status (NCT03681067, NCT03522662). To our knowledge, none of the studies had significant safety issues; the transplant study was terminated due to lack of efficacy.

CMK389 is being developed for its expected immunomodulating activity. Participants treated with CMK389 may be at an increased risk of infection.

Commercially Confidential Information

In addition, administration of CMK389 carries the risk of anaphylaxis and/or hypersensitivity-type reactions.

Commercially Confidential Information

Participants with a history of hypersensitivity to any components of the drug product or with a history of anaphylaxis or serious hypersensitivity syndrome will be excluded.

The risk of an overdose is limited as the drug will be administered by the study personnel and not by the participant.

Commercially Confidential Information

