    - positive hepatitis C antibody (anti-HCV), unless it can be documented that the participant has received highly-effective HCV-specific antiviral therapy, HCV RNA levels are measured, and HCV RNA is undetectable at least 12 weeks after conclusion of HCV-specific antiviral therapy.
5. Any other current or past clinically significant medical condition, including psychiatric condition, which in the Investigator's opinion may interfere with safety of the participant, study objectives or adherence to the protocol.
6. Participants with confirmed abnormal absolute neutrophil count (ANC) of  $<1.5 \times 10^9/L$  or with thrombocytopenia of  $< 75.0 \times 10^9/L$  at screening and baseline (unless baseline visit is omitted).
7. History of malignancy of any organ system (other than localized basal cell carcinoma of the skin), treated or untreated, within the past 5 years, regardless of whether there is evidence of local recurrence or metastases.
8. History of hypersensitivity to any component of the study drug product, or to drugs of similar chemical classes (i.e., IgG-1 related biologic agents).
9. History of severe or serious allergy or hypersensitivity reactions, such as anaphylactic shock, asthma, or uncontrolled urticaria.
10. Donation or loss of 400 mL or more of blood within eight (8) weeks prior to initial dosing, or longer if required by local regulation.
11. Pregnant or nursing (lactating) women, where pregnancy is defined as the state of a female after conception and until the termination of gestation, confirmed by a positive hCG laboratory test.

12. Women of child-bearing potential (WoCBP), defined as all women physiologically capable of becoming pregnant, **unless** they are using highly effective methods of contraception while taking study treatment and for 6 months after last dose. Highly effective contraception methods include:

- Total abstinence (when this is in line with the preferred and usual lifestyle of the participant. Periodic abstinence (e.g. calendar, ovulation, symptothermal, post-ovulation methods) and withdrawal are not acceptable methods of contraception.
- Female sterilization (have had surgical bilateral oophorectomy with or without hysterectomy), total hysterectomy, or tubal ligation at least six weeks before taking study treatment. In case of oophorectomy alone, only when the reproductive status of the woman has been confirmed by follow up hormone level assessment.

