# **10 Safety monitoring and reporting**

## **10.1 Definition of adverse events and reporting requirements**

### **10.1.1 Adverse events**

An adverse event (AE) is any untoward medical occurrence (e.g. any unfavorable and unintended sign [including abnormal laboratory findings], symptom or disease) in a clinical investigation participant after providing written informed consent for participation in the study until the end of the study visit. Therefore, an AE may or may not be temporally or causally associated with the use of a medicinal (investigational) product.

AEs of Special Interest comprise hypersensitivity reactions such as serum sickness and anaphylaxis (as defined by Sampson criterion #1; [Sampson et al 2006](#)).

In addition, all reports of intentional misuse and abuse of the study treatment are also considered an adverse event irrespective if a clinical event has occurred. See [Section 10.1.5](#) for an overview of the reporting requirements.

The occurrence of adverse events must be sought by non-directive questioning of the participant at each visit during the study. Adverse events also may be detected when they are volunteered by the participant during or between visits or through physical examination findings, laboratory test findings, or other assessments.

Abnormal laboratory values or test results constitute adverse events only if they fulfill at least one of the following criteria:

- they induce clinical signs or symptoms,
- they are considered clinically significant,
- they require therapy.

Clinically significant abnormal laboratory values or test results should be identified through a review of values outside of normal ranges/clinically notable ranges, significant changes from baseline or the previous visit, or values which are considered to be non-typical in participant with underlying disease. Investigators have the responsibility for managing the safety of individual participant and identifying adverse events. Alert ranges for liver and kidney related events are included in [Section 16.2](#) and [Section 16.3](#) respectively.

Adverse events must be recorded in the appropriate eCRF capturing AEs under the signs, symptoms or diagnosis associated with them, and accompanied by the following information:

1. The severity grade

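### Routine post-infusion observation is written as a one-hour maximum that can be exceeded, with no minimum in the readable text

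*Protocol*

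**What the plan says.** The routine rule is one sentence in Protocol 6.6.2: "Participants are required to undergo observation for maximum of one hour post-infusion prior to leaving site (or longer if deemed necessary by the investigator".

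The following paragraph of 6.6.2 deals with acute infusion or hypersensitivity reactions and gives two further times:

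- After a reaction: "Participants should be observed for at least four hours after resolution of signs and symptoms".
- After a severe one: "those who have experienced severe infusion reactions should be closely observed for 24 hours after resolution".

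On the hazard itself, Protocol 4.5 says "administration of CMK389 carries the risk of anaphylaxis and/or hypersensitivity-type reactions", and Protocol 10.1.1 says "AEs of Special Interest comprise hypersensitivity reactions such as serum sickness and anaphylaxis". On prior experience, Protocol 4 reports that when the protocol was prepared "only adult healthy volunteers have been exposed to CMK389". Protocol 4.5 adds "CMK389 has not yet been tested in any studies in patients", although that sentence runs into a redaction and its ending is unknown.

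**The concern.** A required observation period protects participants by fixing the least time they stay under supervision after dosing. This sentence fixes the most, then allows the investigator to go beyond it. The ceiling is therefore not a real ceiling, and there is no floor. Observation is mandatory, but its length is left open in the direction that matters.

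What is at stake is early recognition, on site, of an infusion or hypersensitivity reaction in a participant who has no symptoms when the infusion ends. The sponsor names this risk, and the drug had been given only to healthy volunteers. Section 6.6.2 does say that no specific adverse event had been detected, but that statement rests on the same limited experience. Different sites could also read the sentence differently, and a monitor would have no fixed time to check against.

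**Working it through.** No statistical calculation applies: the point involves no alpha, power, effect size or event count, and the plan gives no figure to reproduce. The check is a side-by-side reading.

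**Step 1. Observation times in the readable text**

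| Situation | Lower limit | Upper limit | Source |
|---|---|---|---|
| Routine, after an infusion | None stated | 1 hour, may be exceeded at the investigator's discretion | Protocol 6.6.2, first paragraph |
| After a reaction has resolved | 4 hours | None | Protocol 6.6.2, second paragraph |
| After a severe infusion reaction has resolved | 24 hours | None | Protocol 6.6.2, second paragraph |

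No other readable part of the protocol, including 4.5, 8, 8.4 and 9.1.1, gives a routine post-dose observation time. The SAP gives none either.

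**Step 2. What complies.** Under the first row, a stay of any length above 0 and up to 60 minutes meets the wording, and a stay beyond 60 minutes is allowed if the investigator thinks it necessary. Every positive duration is therefore permitted. The second and third rows do not help, because they apply only after a reaction has been recognised and has resolved.

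**Step 3. Whether another safeguard covers the gap**

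| Safeguard | Source | When it acts |
|---|---|---|
| Exclusion for "History of severe or serious allergy or hypersensitivity reactions, such as anaphylactic shock, asthma, or uncontrolled urticaria" | Protocol 5.2 | Before entry |
| Dosing at the site | Protocol 6.6.1 | During dosing; silent on how long the participant stays |
| Discontinuation, with dosing interrupted at once, for a severe hypersensitivity reaction | Protocol 9.1.1 | After a reaction is recognised |
| Enrolment hold at two or more participants with moderate to severe reactions | Protocol 9.1.4 | After reactions are recognised |
| Independent data monitoring committee reviewing safety data | Protocol 10.2.3 | At defined intervals, at study level |

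None of these sets how long a symptom-free participant remains after an infusion. Only the sentence in 6.6.2 does so.

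**Step 4. How often the sentence applies.** It refers to infusions, so it governs the i.v. arms: 32 on CMK389 plus 8 on placebo, or 40 participants (Protocol 3). The replacement policy in Protocol 9.1.1.1 refers to four doses. The dosing schedule is redacted, so four infusions per i.v. participant is an assumption. On that assumption the sentence covers up to 40 × 4 = 160 infusions, of which 32 × 4 = 128 are active.

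**Step 5. Effect of the correction.** The routine lower limit goes from none stated to 60 minutes if the protocol's own figure is kept as the minimum. The 4-hour and 24-hour times do not change.

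**The case against.** The strongest objection is redaction. In Protocol 4.5 the statement of the hypersensitivity risk is followed at once by blacked-out text, and the assessment schedule in section 8 and the additional assessments in 8.5 are also removed. Administration details are referred to a Pharmacy Manual that was not available. A minimum could sit in any of these, and text missing through redaction cannot be counted as missing from the plan. This stands as a limit on the second half of the point, so the claim is confined to the readable text. It does not rescue the sentence: if a minimum exists elsewhere, sites would hold a protocol maximum alongside another document's minimum, and 6.6.2 would still need aligning.

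A second objection is that sites would naturally read the sentence as a one-hour standard stay that may be extended, that investigators are responsible for participant safety under Protocol 10.1.1, and that nothing suggests anyone would be released after a few minutes. That is fair as a forecast of practice, and the discretion does run in the safe direction. But a safety instruction should not depend on readers correcting it, and the literal wording permits the short stay.

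A third objection is that 60 minutes is not stated anywhere as a minimum. That is correct. It is the protocol's own figure with the direction reversed, and the right duration is a clinical decision for the sponsor.

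Finally, this is probably one wrong word with no effect on the results. That also stands, and it is why the point is rated minor.

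**Conclusion.** The concern holds. The operative sentence in Protocol 6.6.2 sets a ceiling that it immediately allows to be exceeded, and no routine minimum appears in the readable protocol or SAP. It is a small participant-safety correction that should be made. No harm or missed reaction is shown, and the sample size, power, estimand and analysis are untouched.

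Two qualifications apply. The absence of a minimum is established only for the text that can be read. That *maximum* was meant as *minimum* is likely, but the documents do not show it; if up to one hour was intended, the sentence still lacks a floor and still needs correcting. Confidence is medium for these reasons.

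**What to change.** In Protocol 6.6.2, change the routine requirement from a maximum of one hour to at least one hour after the infusion, or to another minimum that the sponsor's clinical team confirms. Keep the investigator's discretion to extend. If the redacted text or the Pharmacy Manual already sets a minimum, use that figure so that the documents agree.

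The cost is a few words in a protocol clarification or amendment and, at most, slightly longer site visits.
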